3.1 Eligibility Criteria

- 3.1.1 Patients must have histologically or cytologically confirmed LCH, ECD or HS. Confirmation of outside pathology at BWH will be performed but is not mandatory prior to study enrollment (see section 3).
- 3.1.2 Detectable disease by at least one of the following modalities: CT, PET, bone scan, or MRI.
- 3.1.3 Patients with LCH must require systemic therapy according to the Histiocyte Society LCH Evaluation and Treatment Guidelines (HS 2009) Or Patients with HS requiring systemic treatment as defined by disease that cannot be surgically resected and/or encompassed in a single radiation field.
- 3.1.4 Age 18 years or older.
- 3.1.5 ECOG performance status ≤ 2 (Karnofsky $\geq 60\%$, see Appendix A)
- 3.1.6 Participants must have normal organ and marrow function as defined below:

_	absolute neutrophil count	≥1,000/mcL
_	platelets	≥100,000/mcL
-	total bilirubin	within 1.5 times normal institutional limits
-	AST(SGOT)/ALT(SGPT)	$\leq 3 \times$ institutional upper limit of normal
-	creatinine	within 2 times normal institutional limits
		OR
-	creatinine clearance	\geq 30 mL/min/1.73 m ² . Note, dose adjustments are
		required for $CrCl \ge 30$ mL/min but ≤ 60 ml/min.

- 3.1.7 Able to take aspirin 81 mg daily as prophylactic anticoagulation if not on warfarin, low molecular weight heparin or oral factor Xa inhibitor. Patients intolerant to ASA may use warfarin or low molecular weight heparin at doses designed to treat deep venous thrombosis.
- 3.1.8 All study participants must be registered into the mandatory Revlimid REMS® program, and be willing and able to comply with the requirements of the REMS® program.

- 3.1.9 Women of child-bearing potential and men must agree to use adequate contraception (hormonal or barrier method of birth control; abstinence) prior to study entry and for the duration of study participation.
- 3.2.0 Ability to understand and the willingness to sign a written informed consent document.

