1. OBJECTIVES

This is an open-label phase II study to evaluate the efficacy and safety of lenalidomide in participants with relapsed/refractory ECD or LCH and in any patient with HS requiring systemic therapy. Patients will receive up to 12 cycles of lenalidomide with treatment occurring on days 1-21 of each 28 day cycle. In cycle one patients will receive lenalidomide 10 mg daily due to the unknown incidence of tumor flare in this population (tumor flare has been observed in other diseases such as chronic lymphocytic leukemia). Patients who tolerate the 10 mg dose well will be escalated to 25 mg for future cycles. There will also be the possibility of dose reduction for patients who do not tolerate the 10 mg starting dose. Dosage thereafter will be adjusted based upon toxicity. Lenalidomide is known to increase the risk of venous and arterial thromboembolic events. Patients not already receiving systemic anticoagulation for other clinical indications will be required to take aspirin 325 mg daily for the duration of the protocol or for one month following treatment discontinuation, whichever is longer.

Disease assessments will occur at baseline and then again at cycle 3 day 1, cycle 6 day 1, cycle 9 day 1 and cycle 12 day 1 as well as every 3 months thereafter until month 24 from study initiation when disease assessment will occur every 6 months until month 36 from the initiation of treatment. Disease assessments will consist initially of an MRI of the brain/pituitary and PET/CT (although a CT of the chest, abdomen and pelvis along with a bone scan is allowed if PET/CT is rejected by insurance). Clinical documentation of skin lesions with photography is highly encouraged. Measurement and documentation of all skin lesions is required even if photography is not performed. A repeat MRI is not required beyond baseline if the MRI at baseline is normal and there is no clinical suspicion of CNS or pituitary involvement. A bone marrow biopsy is only required if the patient has at least one cytopenia of grade 2 or greater at baseline or has evidence of bone marrow involvement on PET/CT. The bone marrow biopsy only needs to be repeated if abnormal at baseline.

Patients will be followed for 3 years (thirty-six months) from the initiation of therapy or until they initiate a new therapy for their underlying disease, whichever occurs first.

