1.1 Study Design

This is a single agent, phase II open-label study of single agent lenalidomide in patients with relapsed/refractory ECD, LCH, or HS.

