1.2 Primary Objectives

To estimate the response rate of patients with relapsed/refractory ECD, LCH, and HS with single agent lenalidomide.

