2. BACKGROUND

2.1 Study Disease(s)

Langerhans Cell Histiocytosis (LCH) is a rare disease (1-10 cases per million) of unknown etiology distinguished by the clonal proliferation of pathologic histiocytes derived from bone marrow dendritic cells (1). BRAF mutations have been identified in approximately 50% of cases but the inciting event remains unclear (2). Clinical manifestations are related to the pattern of infiltration or organ involvement which is heterogeneous, can involve single or multiple organs, and can be associated with varying, often unpredictable outcomes ranging from spontaneous regression to multiple episodes of reactivation, long term debilitating sequelae, rapid progression, and death.

The natural history of LCH is ill defined in adults. Studies of disease outcomes have been primarily undertaken in the pediatric population [3]. Assessments of adult patients with LCH have reported death events in 28-32% of patients with 4-6.5 year follow up [4,5]. There is no agreed standard of care in adults for either first-line or reactivation disease. As such, there is an unmet need for a well-tolerated, efficacious agent to treat adult LCH.

A recently completed international adult study (LCH-A1) attempted to define and implement a uniform treatment approach in adults with respect to smoking cessation and the use of prednisone, vinblastine, and 6-mercaptopurine. Although final analysis of the data have not been completed at the present time, preliminary analysis indicates that many adult patients were unable to tolerate the standard pediatric multi-agent regimen of prednisone and vinblastine, due to neuropathy attributable to the latter agent. This was corroborated at Baylor College of Medicine where a study of vinblastine in LCH was terminated early when 5 or the first 7 adults treated developed Grade 3-4 toxicity at some point during therapy, and only 2/7 patients were able to complete the treatment course as prescribed by the protocol. Within a median of 6 months after starting therapy, 3/6 patients were in remission and 3/6 had active disease [6].

Reported disease reactivation rates after frontline therapy in adults vary widely. Multisystem LCH reactivation has been reported in 26-43% of patients [4, 7, 8] treated with a variety of

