3. PARTICIPANT SELECTION

Patients aged 18 or older with histologically confirmed Langerhans cell histiocytosis, Erdheim-Chester disease, or histiocytic sarcoma will be eligible. Confirmation of pathology at Brigham and Women's Hospital is preferred but patients may be enrolled based upon outside review of pathology if in the opinion of the principle investigator the pathology is consistent with LCH, ECD, or HS and if a delay in treatment due to review of pathology at BWH would be detrimental to the patient. Tissue will be requested for Oncopanel testing on all patients but this is not an eligibility criteria. Patients will be consented to DFCI protocol 11-104 for Oncopanel testing. Patients who decline participation in this companion protocol will not have material sent for Oncopanel.

Patients with LCH must require systemic treatment according to the Histiocyte Society LCH Evaluation and Treatment Guidelines (2009). There is no limit on the number of prior therapies received so long as the patient otherwise meets eligibility criteria. Patients with HS that cannot be surgically excised and/or encompassed in a radiation field will be eligible even if they have not received prior systemic therapy.

Laboratory tests required for eligibility must be completed within 14 days of registration and radiographic tests must be completed within 30 days of registration.

Since the response criteria differ for histiocyte disorders than for other malignancies, radiographically detectable disease is required but does not need to be bidimensionally measurable as in Cheson criteria.

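### The stated population is relapsed/refractory LCH and ECD, but no eligibility criterion requires prior therapy for either disease, and criterion 3.1.3 has no ECD condition

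*Combined protocol and SAP*

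**What the plan says.** **Objectives and design.** The primary objective (1.2) is "To estimate the response rate of patients with relapsed/refractory ECD, LCH, and HS with single agent lenalidomide". Section 1.1 describes a "phase II open-label study of single agent lenalidomide in patients with relapsed/refractory ECD, LCH, or HS". Section 1 is narrower for one disease and wider for another: "participants with relapsed/refractory ECD or LCH and in any patient with HS requiring systemic therapy".

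**Eligibility.** Criterion 3.1.1 reads "Patients must have histologically or cytologically confirmed LCH, ECD or HS", with no condition on line of therapy. Criterion 3.1.3 has two branches joined by an 'or'. The LCH branch is "Patients with LCH must require systemic therapy according to the Histiocyte Society LCH Evaluation and Treatment Guidelines (HS 2009"). The HS branch is "Patients with HS requiring systemic treatment as defined by disease that cannot be surgically resected and/or encompassed in a single radiation field". There is no ECD branch. On prior treatment, section 3 says "There is no limit on the number of prior therapies received so long as the patient otherwise meets eligibility criteria", which removes a maximum and sets no minimum. Section 3 also states that HS patients may enter without having had systemic therapy. The exclusions in 3.2 that touch prior treatment are a washout (3.2.1) and the rules on earlier lenalidomide and thalidomide (3.2.3).

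**Registration.** Under 4.2 a patient is registered against a checklist that reflects the inclusion and exclusion criteria, and must meet all of them.

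**Statistics.** Section 13.1 names the endpoint population as patients with LCH, without ECD, HS or any mention of relapsed/refractory disease. It plans 12 patients, calls the treatment worthy of further study at three or more responses, and treats a 5% response rate in this population as unworthy.

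**The concern.** A single-arm trial has no internal comparator. Its result is read against a fixed reference rate, here 5%, and that reading is valid only for the population the reference was chosen for. If the eligibility list is wider than the objective, the observed proportion estimates response in whatever mixture happens to enrol.

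With 12 patients, two or four from outside the intended population are a large share of the data. Stratification is given as not applicable (13.3), and sections 13.5 to 13.7 plan no analysis by prior therapy, so the planned analysis would not separate the groups. The result decides whether a larger phase II trial is proposed, so it matters which patients it describes.

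**Working it through.** **Step 1. Set the population statements side by side.**

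| Place | LCH | ECD | HS |
|---|---|---|---|
| 1 | relapsed/refractory | relapsed/refractory | any needing systemic therapy |
| 1.1, 1.2 | relapsed/refractory | relapsed/refractory | relapsed/refractory |
| 3 | needs systemic therapy; no minimum prior therapy | named as eligible; no further condition | not resectable or irradiable; untreated allowed |
| 3.1.1 | confirmed diagnosis | confirmed diagnosis | confirmed diagnosis |
| 3.1.3 | needs systemic therapy | no condition stated | not resectable or irradiable |
| 3.2 | washout and prior-IMiD rules only | same | same |
| 13.1 | named, no line of therapy | not named | not named |

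Three mismatches follow. LCH and ECD are restricted to relapsed/refractory in sections 1, 1.1 and 1.2 but not in any criterion. HS is relapsed/refractory in 1.1 and 1.2 but may be untreated in 1 and 3. The endpoint in 13.1 names one disease of the three.

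**Step 2. Reproduce the plan's own figures (13.1).** Exact 90% limits for x responses in n = 12 are the 5% quantile of Beta(x, 13 − x) and the 95% quantile of Beta(x + 1, 12 − x).

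- x = 3: 7.2% to 52.7%. The plan states 7–53%, which agrees.
- x = 2: 3.0% to 43.8%, which contains 5%, while the interval for x = 3 does not. The plan's statement that two is the largest such count also agrees.

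The issue is therefore the population, not the arithmetic.

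**Step 3. Chance of passing the rule if every patient is at 5%.**

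P(X ≥ 3) = 1 − [0.95¹² + 12(0.05)(0.95¹¹) + 66(0.05²)(0.95¹⁰)] = 1 − (0.5404 + 0.3413 + 0.0988) = 0.0196, or 2.0%.

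**Step 4. Illustration with untreated patients in the cohort.** Let k of the 12 be untreated with response probability p, and the other 12 − k be at 5%. Then X = Bin(k, p) + Bin(12 − k, 0.05). The documents give neither k nor p, so both are assumed, with p from 10% to 30%.

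Example, k = 2 and p = 0.30. The untreated pair gives 0, 1 or 2 responses with probability 0.49, 0.42 and 0.09. The other ten give at least 3, 2 or 1 responses with probability 0.0115, 0.0861 and 0.4013.

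P(X ≥ 3) = 0.49(0.0115) + 0.42(0.0861) + 0.09(0.4013) = 0.0056 + 0.0362 + 0.0361 = 0.078.

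| Untreated of 12 | p = 10% | p = 15% | p = 30% |
|---|---|---|---|
| 0 | 2.0% | 2.0% | 2.0% |
| 1 | 2.4% | 2.8% | 4.1% |
| 2 | 2.9% | 3.9% | 7.8% |
| 4 | 4.1% | 6.9% | 19.8% |

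These figures show a direction and a possible size. They do not forecast who will enrol, and the mismatch in Step 1 does not depend on them.

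**The case against.** **The intent is clear.** Waiving prior systemic therapy for HS in section 3 makes sense only if LCH and ECD patients are expected to have had it, and section 1 says so directly. This stands as evidence of intent. It does not close the gap, because registration under 4.2 turns on the listed criteria, and an inference from an HS exemption is not one of them. The checklist itself is not in the documents, so it may ask more than the criteria do.

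**ECD is admitted.** A reader might infer from 3.1.3, taken literally with all criteria mandatory, that no ECD patient can qualify. The documents do not support that. Criterion 3.1.3 is worded disease by disease, while section 3, criterion 3.1.1 and section 5.2.1 all admit ECD. The practical gap is that ECD has no stated need-for-treatment condition.

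**Spontaneous regression.** Section 2.1 describes LCH as having "varying, often unpredictable outcomes ranging from spontaneous regression to multiple episodes of reactivation". A reader might infer that untreated patients will respond more often regardless of drug. The documents do not say this: the sentence covers the whole LCH spectrum and does not compare untreated with relapsed disease. LCH entrants must still require systemic therapy, all entrants need detectable disease (3.1.2), and responses should last at least 8 weeks (11.1.2.3). Inflation of the response rate is therefore possible but not shown.

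**Scale.** This is a single-center pilot. An investigator confirms eligibility (4.1), and treatment history is recorded in detail (5.2.1), so results by prior therapy could be reported. Section 13.1 accepts a risk of overestimating response, though it attributes that to sample size. These points lower the severity but leave the mismatch in place.

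**Conclusion.** The point holds as an inconsistency in the study population. The objective and design describe relapsed/refractory disease. No criterion carries that requirement for LCH or ECD, 3.1.3 is silent on ECD, HS is described in two ways, and 13.1 names LCH alone. Following the criteria as written, untreated LCH or ECD patients can be registered. The response proportion and the 3-of-12 rule would then not answer the stated question.

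The claim is conditional: the documents show that such patients can enter, not that any will. The illustrated rise from 2.0% to about 3–8% with two untreated patients, or 4–20% with four, assumes response rates of 10–30% in those patients and reads 5% as the rate in relapsed/refractory disease. Section 13.1 ties the 5% only to its own patient population. With one untreated patient at 10% the figure is 2.4%, barely different from 2.0%. This should be fixed, but it does not invalidate the design, and the plan's confidence limits are correct.

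**What to change.** Reconcile sections 1, 1.1, 1.2, 3, 3.1.3 and 13.1 to one population. To match the evident intent:

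- **3.1.3 and section 3:** state that LCH and ECD patients must have relapsed after, or be refractory to, prior systemic therapy. Keep the existing LCH need-for-treatment condition and give ECD an explicit branch.
- **1.1 and 1.2:** describe the population as relapsed/refractory LCH or ECD, and HS requiring systemic therapy.
- **13.1:** name the same three diseases in the primary endpoint.
- **Eligibility checklist:** carry the same wording.

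The cost is a few sentences and a checklist line, with possibly slightly slower accrual if untreated LCH or ECD patients had been expected. The sample size and the decision rule do not change.

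If untreated LCH or ECD patients are in fact intended, the sponsor should instead change the stated objective, confirm that the 5% reference still applies to the wider population, and report responders by prior therapy (none versus at least one). ECD still needs its own branch in 3.1.3, and 13.1 still needs aligning. This route is not free, because it changes the primary question and reopens the choice of reference rate.

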3.2 Exclusion Criteria

- 3.2.1 Prior chemotherapy or radiation within 2 weeks (6 weeks for nitrosoureas or mitomycin C) prior to entering the study or those who have not recovered from adverse events due to agents administered more than 2 weeks earlier.
- 3.2.2 Participants who are receiving any other investigational agents.
- 3.2.3 Prior treatment with lenalidomide. Patients previously treated with thalidomide who discontinued treatment for reasons aside from an adverse reaction to thalidomide are permitted.
- 3.2.4 History of another invasive malignancy unless treated with curative intent 5 years or more prior to study entry. Patients with localized carcinoma of the cervix, non-melanoma skin cancer, or early stage prostate cancer requiring observation only are eligible regardless of timing of diagnosis.
- 3.2.5 Uncontrolled intercurrent illness including, but not limited to, ongoing or active infection, symptomatic congestive heart failure, unstable angina pectoris, cardiac arrhythmia, or psychiatric illness/social situations that would limit compliance with study requirements.
- 3.2.6 Pregnant women are excluded from this study because lenalidomide has known teratogenic effects. Because there is an unknown but potential risk for adverse events in nursing infants secondary to treatment of the mother with lenalidomide, breastfeeding should be discontinued if the mother is treated with lenalidomide.
- 3.2.7 Known active hepatitis B (HBV) or hepatitis C (HCV) infection. Patients who are positive only for HBV surface antibody as a result of prior vaccination are eligible. Patients with a positive HBV core antibody but undetectable HBV viral load are eligible.
- 3.2.8 HIV-positive participants on combination antiretroviral therapy are ineligible because of the potential for pharmacokinetic interactions with lenalidomide. In addition, these participants are at increased risk of lethal infections when treated with marrow-suppressive therapy. Appropriate studies will be undertaken in participants receiving combination antiretroviral therapy when indicated.
- 3.2.9 Concomitant corticosteroids unless patient has been on a stable dose of prednisone (or equivalent) of ≤ 10 mg daily for at least 2 weeks prior to first dose of study drug.
- 3.2.10 Inability to swallow pills.

3.3 Inclusion of Women and Minorities

Both men and women of all races and ethnic groups are eligible for this trial.

4. REGISTRATION PROCEDURES

4.1 General Guidelines for DF/HCC and DF/PCC Institutions

Institutions will register eligible participants with the DF/HCC Quality Assurance Office for Clinical Trials (QACT) central registration system. Registrations must occur prior to the initiation of protocol therapy. Any participant not registered to the protocol before protocol therapy begins will be considered ineligible and registration will be denied.

An investigator will confirm eligibility criteria and a member of the study team will complete the QACT protocol-specific eligibility checklist.

Following registration, participants may begin protocol therapy. Issues that would cause treatment delays should be discussed with the Overall Principal Investigator (PI). If a participant does not receive protocol therapy following registration, the participant's registration on the study must be canceled. Notify the QACT Registrar of registration cancellations as soon as possible.

4.2 Registration Process for DF/HCC and DF/PCC Institutions

The QACT registration staff is accessible on Monday through Friday, from 8:00 AM to 5:00 PM Eastern Standard Time. In emergency situations when a participant must begin protocol therapy during off-hours or holidays, call the QACT registration line at [contact] and follow the instructions for registering participants after hours.

The registration procedures are as follows:

- Obtain written informed consent from the participant prior to the performance of any protocol specific procedures or assessments.
- Complete the QACT protocol-specific eligibility checklist using the eligibility assessment documented in the participant's medical record and/or research chart. To be eligible for registration to the protocol, the participant must meet all inclusion and exclusion criterion as described in the protocol and reflected on the eligibility checklist.

Reminder: Confirm eligibility for ancillary studies at the same time as eligibility for a treatment protocol. Registration to both treatment and ancillary protocols will not be completed if eligibility requirements are not met for all studies.

- Fax the eligibility checklist(s) and all pages of the consent form(s) to the QACT at [contact]. For Phase I protocols, attach participant dose level assignment confirmation from the sponsor.
- The QACT Registrar will (a) review the eligibility checklist, (b) register the participant on the protocol, and (c) randomize the participant when applicable.
- An email confirmation of the registration and/or randomization will be sent to the Overall PI, study coordinator(s) from the Lead Site, treating investigator and registering person immediately following the registration and/or randomization.

4.3 General Guidelines for Other Investigative Sites

N/A

4.4 Registration Process for Other Investigative Sites

N/A

5. TREATMENT PLAN

Treatment will be administered on an outpatient basis. Expected toxicities and potential risks as well as dose modifications for lenalidomide are described in Section 6 (Expected Toxicities and Dosing Delays/Dose Modification). No investigational or commercial agents or therapies other than those described below may be administered with the intent to treat the participant's malignancy.

5.1 Treatment Regimen

For cycle 1, lenalidomide will be administered at a dose of 10 mg daily on days 1-21 of a 28 day cycle. Patients will be assessed for toxicity between days 22 and 28. If no grade 3 or greater toxicity has occurred the dose will be escalated to 25 mg daily on days 1-21 of a day 28 cycle (patients with a baseline CrCl of 30 to ≤ 60 will stay at the 10 mg dose). Patients with a baseline CrCl of 30 to ≤ 60 can be dose escalated to 25 mg if there is no grade 3 or greater toxicity at week 8 visit if CrCl has improved to >60. No dose escalated unless it is a toxicity due to neutropenia in which case the dose can be escalated if there is no recurrent neutropenia with growth factor support for two continuous cycles. Treatment will be administered on an outpatient basis. The maximum number of cycles is 12 (inclusive of cycle 1 and/or 2 dosing at 10 mg). Reported adverse events and potential risks are described in Section 7. Appropriate dose modifications are described in Section 6. No investigational or commercial agents or therapies other than those described below may be administered with the intent to treat the participant's malignancy.

Agent	Premedications; Precautions	Dose	Route	Schedule	Cycle Length
Lenalidomide	None	10 mg tablet (cycle 1)*	PO at approximately the same time each day(+/- 2 hours)	Days 1-21	28 days
Lenalidomide	None	25 mg tablet (cycle 2 and subsequent)*	PO at approximately the same time each day	Days 1-21	

The participant will be requested to maintain a medication diary of each dose of medication. The medication diary will be returned to clinic staff at the end of each cycle.

5.2 **Pre-Treatment Criteria**

5.2.1 Cycle 1, Day 1

Participants must meet all of the inclusion criteria, have none of the exclusion criteria, and must be registered to the protocol prior to initiating therapy.

The following studies and evaluations should be carefully reviewed to determine the patient's suitability to initiate study treatment.

- 1. Diagnosis of LCH, ECD, or HS is established by disease evaluations and laboratory studies and confirmed histologically
 - 2. Complete physical examination.
 - 3. Medical history: Detailed documentation of disease and treatment history with outcomes.
 - 4. Performance status $\geq 60\%$
 - 5. Concurrent medical conditions.
 - 6. Hematology: CBC with automated differential.

- 7. Serum chemistries: Albumin, alkaline phosphates, total bilirubin, bicarbonate, BUN, calcium, chloride, creatinine, glucose, potassium, total protein, SGOT [AST], SGPT [ALT], sodium.
- 8. Baseline adverse event assessment from time of signing informed consent.

